6.4.3. Medical Conditions

The reported adverse event or serious adverse event will be recorded in CRF. A collective data of incidence of adverse events will be provided in the clinical study report.

6.5. Concomitant Medications

The details of concomitant medication prescribed and used will be referred from CRF. The list of concomitant medication/ drugs will be provided in the clinical study report.

7. SAFETY ANALYSES

The safety analyses will be based on the safety population, unless otherwise specified.

Descriptive statistics will be used to assess safety and tolerability objectives. No formal statistical analyses of safety data are planned. Data will be summarized and listed according to Accutest Data Standards and statistical principles.

7.1. Adverse Events Analyses

Adverse events analyses including the analysis of adverse events (AEs), Serious adverse events (SAEs) and other significant AEs will be based on Accutest Data Standards.

7.2. Clinical Laboratory Analyses

The analysis of laboratory safety test results will be based on GSK Core Data Standards, unless otherwise specified. The details of these are presented in [Appendix 1: Schedule of Activities](#).

7.3. Other Safety Analyses

The analyses of non-laboratory safety test results including ECGs and vital signs will be based on GSK Core Data Standards, unless otherwise specified. The details of the planned displays are presented in [Appendix: List of Data Displays](#).

8. PHARMACOKINETIC ANALYSES

8.1. Primary Pharmacokinetic Analyses

8.1.1. Endpoint / Variables

8.1.1.1. Drug Concentration Measures

Refer to Appendix : Data Display Standards & Handling Conventions (Section 10.3.3 Reporting Standards for Pharmacokinetic)

8.1.1.2. Derived Pharmacokinetic Parameters

Pharmacokinetic parameters will be calculated by standard non-compartmental analysis according to current working practices and using the currently supported version of SAS version 9.4. All calculations of non-compartmental parameters will be based on actual sampling times. Pharmacokinetic parameters listed will be determined from concentration-time data, as data permits.

Parameter	Parameter Description
C_{max}	Maximum observed drug concentration during the study.
AUC_{0-t}	Area under the plasma concentration - time curve measured to the last quantifiable concentration, using the linear trapezoidal rule.
AUC_{0-inf}	AUC_{0-t} plus additional area extrapolated to infinity, calculated using the formula $AUC_{0-t} + C_t/K_{el}$, where C_t is the last measurable drug concentration and K_{el} is the elimination rate constant.
T_{max}	Time to observe maximum drug concentration. If the maximum value occurs at more than 1 time point, T_{max} is defined as the first time point with this value.
AUC_{0-t}/AUC_{0-inf}	Ratio of AUC_{0-t} and AUC_{0-inf}
Residual area	Extrapolated area $(AUC_{0-inf} - AUC_{0-t})/ AUC_{0-inf}$
K_{el}	Apparent first – order terminal elimination rate constant calculated from a semi-log plot of the plasma concentration versus time curve, using the method of least square regression.
$t_{1/2}$	Terminal half-life as determined by quotient $0.693/K_{el}$
Vd	Fluid volume that would require to contain the whole drug in the body at the same conc. found in the plasma is given by formula, $Dose / (K_{el} \times AUC_{0-inf})$
CL	Clearance of a given individual in the measure of his body capacity to eliminate a drug and is given by formula $Dose / AUC_{0-inf}$

NOTES:

- Additional parameters may be included as required.
- The pharmacokinetic parameters will not be calculated in case of inconclusive concentration time profile (e.g. lack of sufficient measurable concentrations).
- No value of K_{el} , Residual area, AUC_{0-t}/AUC_{0-inf} , AUC_{0-inf} , Vd, CL and $t_{1/2}$ will be reported for cases that do not exhibit a terminal log-linear phase in the concentration versus time profile

8.1.2. Summary Measure

Parameters C_{max} , AUC_{0-t} and AUC_{0-inf} will be applicable for BE demonstration and Parameters C_{max} , and AUC_{0-t} for dose proportionality. These parameters will be calculated for each participant-formulation combination using the non-compartmental model by using statistical package SAS® 9.4

8.1.3. Population of Interest

The primary pharmacokinetic analyses will be based on the BE Analysis Set population, unless otherwise specified.

8.1.4. Statistical Analyses / Methods

Details of the planned displays are provided in Appendix: List of Data Displays and will be based on Accutest Data Standards and statistical principles.

Unless otherwise specified, endpoints / variables defined in Section 8.1.1 will be summarised using descriptive statistics, graphically presented (where appropriate) and listed.

8.1.4.1. Statistical Methodology Specification

The following pharmacokinetic statistical analyses will only be performed if sufficient data is available (i.e. if participants have well defined plasma profiles).

Endpoint / Variables
Primary end points for BE Demonstration (T1 vs. R): C _{max} , AUC _{0-t} and AUC _{0-inf} Primary end points for dose proportionality (T2 vs. T1) :C _{max} , AUC _{0-t}
Model Specification
ANOVA will be performed on Log-transformed C _{max} , AUC _{0-t} and AUC _{0-inf} using Proc Mixed Model. Model LC _{max} or LAUC _{0-t} or LAUC _{0-inf} = sequence period treatment (fixed factors) and random: Participant (Sequence) (random factor)]
Model Checking & Diagnostics
A separate ANOVA model will be used to analyze each of the parameters. All main effects will be tested against the residual error (mean square error) from the ANOVA model as the error term. Each analysis of variance will also include calculation of least-square means, adjusted differences between formulation means and the standard error associated with these differences. 
 • For the Proc Mixed Model, model assumptions will be checked, and appropriate adjustments may be applied based on the data. • Distributional assumptions underlying the model used for analysis will be examined by obtaining a normal probability plot of the residuals and a plot of the residuals versus the fitted values (i.e. checking the normality assumption and constant variance assumption of the model respectively) to gain confidence that the model assumptions are reasonable. • Non-parametric analyses will be conducted on un-transformed parameter T_{max}.
Model Results Presentation
Bioequivalence will be concluded if: The 90% confidence interval of geometric mean ratio of log-transformed C _{max} , AUC _{0-t} and AUC _{0-inf} between test (T1) and reference (R) products fall within the range of 80.00% to

125.00% for Griseofulvin.

Dose proportionality will be concluded if:

The 90% confidence interval of geometric mean ratio of log-transformed AUC_{0-t} and C_{max} between test (T2) and test (T1) products falls within the range of 80.00% to 125.00% for Griseofulvin.

10. APPENDICES

10.1. Appendix 1: Schedule of Activities

10.1.1. Protocol Defined Schedule of Events

[figure not shown]
[figure not shown]
Procedure	Screening (within 21 days prior to dosing of period-I)	First Period						Washout [at least 7 days (not more than 14 days) between subsequent dosing] Day 6
		Check-in Day -1	Dosing day Day 1	Checkout day Day 2	Ambulatory sample visit			
					Day 3	Day 4	Day 5	
Issue of Participant informed consent form	X							
Breath Alcohol test ^{a, c}	X	X				X	X	X
Questionnaire about smoking ^c		X				X	X	X
Weight ^a	X							
Height ^a	X							
Medical / clinical history ^a	X	X						
Vital Signs measurement ^{a, b, i}	X	X	X	X	X	X	X	X
Physical examination ^{a, b, i}	X	X		X				
12 Lead ECG ^a	X							
Serology ^a	X							
Haematology ^{a, i}	X							
Biochemistry ^{a, i}	X							

ALT (Alanine transaminase) test ^e		X						
Urinalysis ^{a,i}	X							
Serum pregnancy test for female ^e		X						
Urine examination for drugs of abuse ^h		X						
Admit to Clinical Research Center		X						
Meals ^d		X	X					
Study medication administration ^f			X					
PK Samples ^g			X	X	X	X	X	
Concomitant medication	_____→							
AE		_____→						
SAE		_____→						

Procedure	Second Period						Washout [at least 7 days (not more than 14 days) between subsequent dosing] Day 13
	Check-in Day 7	Dosing day Day 8	Checkout day Day 9	Ambulatory sample visit			
				Day 10	Day 11	Day 12	
Issue of Participant informed consent form							
Breath Alcohol test ^{a, c}	X			X	X	X	
Questionnaire about smoking ^c	X			X	X	X	
Weight ^a							
Height ^a							
Medical / clinical history ^a	X						
Vital Signs measurement ^{a, b, i}	X	X	X	X	X	X	
Physical examination ^{a, b, i}	X		X				
12 Lead ECG ^a							
Serology ^a							
Haematology ^{a, i}							
Biochemistry ^{a, i}							
ALT test ^c	X						
Urinalysis ^{a, i}							
Serum pregnancy test for female ^c	X						

Urine examination for drugs of abuse ^h	X						
Admit to Clinical Research Center	X						
Meals ^d	X	X					
Study medication administration ^f		X					
PK Samples ^g		X	X	X	X	X	
Concomitant medication	_____→						
AE	_____→						
SAE	_____→						

Procedure	Third Period						Post Study (Day 19)
	Check-in Day 14	Dosing day Day 15	Checkout day Day 16	Ambulatory sample visit			OR Early Discontinuation of Participant ^M
				Day 17	Day 18	Day 19	
Issue of Participant informed consent form							
Breath Alcohol test ^{a, c}	X			X	X	X	
Questionnaire about smoking ^c	X			X	X	X	
Weight ^a							
Height ^a							
Medical / clinical history ^a	X						
Vital Signs measurement ^{a,b, i}	X	X	X	X	X	X	X
Physical examination measurement ^{a,b, i}	X		X				X
12 Lead ECG ^a							
Serology ^a							
Haematology ^{a, i}							X
Biochemistry ^{a, i}							X
ALT test ^e	X						
Urinalysis ^{a, i}							X
Serum pregnancy test	X						X

for female ^e							
Urine examination for drugs of abuse ^h	X						
Admit to Clinical Research Center	X						
Meals ^d	X	X					
Study medication administration ^f		X					
PK Samples ^g		X	X	X	X	X	
Concomitant medication							
AE							
SAE							

Note: Additionally, any other assessment including laboratory test(s) will be done if judged necessary by the Principal Investigator (PI) or medical officer at any time during the course of study.

- a. Breath alcohol test, demographic data (Weight, Height and BMI), medical / clinical history, physical examination including vital signs, 12-lead Electrocardiogram (ECG), Haematology, biochemistry, serology (HIV, Hepatitis B and C) and urinalysis will be performed at screening.
- b. Physical examination and vital signs examination (blood pressure, pulse rate, respiration rate and body temperature) will be done at check-in and check-out of each study period.

Physical examination and vital examination can be started approximately 02.00 hours prior to the scheduled time in each study period.

Intravenous cannula site will be observed by principal investigator/co-investigator /Sub-investigator /medical officer for any swelling or thrombophlebitis.

Measurement of Vital signs (blood pressure, pulse rate, respiration rate and body temperature) will be done at pre-dose and at 01.00, 03.00, 05.00, 08.00hrs ± 45 minutes of scheduled time in each study period and at each ambulatory visits.

- c. Breath alcohol test and questionnaire about smoking (history of smoking) will be carried out before check-in and before each ambulatory blood sample collection for each study period.
- d.
 - Standardized meal will be given during check-in night. The check-in night dinner will be served in a way to maintain at least 10.00 hours fasting before receiving high-fat and high-calories breakfast.
 - On dosing day, standardized high-fat and high-calories breakfast will be given 30 minutes prior to drug administration. Participants should eat the high-fat and high-calorie breakfast completely within 25 minutes.
 - Participants will be given standardized meal at around 04.00, 09.00 and 13.00 hours post-dose.
- e. For all participants, ALT will be done before check-in for each study period. For female participants,

serum pregnancy test (Serum (β) Beta- hCG) will be done before check-in for each study period.

- f.** Single oral dose of the either of two test product or reference product will be administered as per randomization with 240 ± 2 mL of water at ambient temperature under fed condition.
- g.** Total number of blood samples (5 mL per sample): 22 per period.

Sampling times: Pre-dose (collected within 01.00 hour prior to dosing) and at 00.50, 01.00, 01.50, 02.00, 02.50, 03.00, 03.50, 04.00, 04.50, 05.00, 05.50, 06.00, 06.50, 07.00, 08.00, 10.00, 12.00, 24.00, 48.00, 72.00 and 96.00 hours post dose. The detailed description on blood sample collection is provided in section 8.5 Pharmacokinetics.

Blood samples will be collected in Na-Heparin Vacutainer.

Blood samples after 24.00 hours will be collected on ambulatory basis.

- h.** Urine examination for drugs of abuse test will be done on check-in Day for each study period.
- i.** Physical examination, measurement of blood pressure, pulse rate, respiration rate and body temperature, serum pregnancy test (Serum (β) Beta- hCG) (for female participants), Haematology, biochemistry and urinalysis will done at post study or on early discontinuation of participant.

√ indicates the occurrence, * indicates day starts from post-dose.

10.2. Appendix 2: Study Phases and Treatment Emergent Adverse Events

10.2.1. Study Phases for Treatment Emergent Adverse Events and Concomitant Medication

Subject. No.	
Study Period	
Age (years)	
Sex	
Adverse Event	
Date & Time of Onset	
Date & Time of Reporting	
Severity	
Seriousness	
Action Taken	
Outcome	
Causality assessment	
Likelihood	
Date & Time of Resolution	
Date & Time of Last Dose Administered	
Last Investigational Medicinal Product Administered	
Concomitant Treatment	

10.3. Appendix 3: Data Display Standards& Handling Conventions

10.3.1. Reporting Process

Software

 The currently supported versions of SAS software (Version 9.4) will be used.
Analysis Datasets

 SDTM datasets will be created according to CDISC standards (SDTM IG Version 3.2).
Generation of RTF Files

 RTF files will not be generated.
Generation of xlm Files

 xlm files will not be generated.

10.3.2. Reporting Standards

Planned and Actual Time	

 Reporting for tables, figures and formal statistical analyses: Sampling time deviations will be considered during the calculation of pharmacokinetic parameters. Graphical summaries for individual subjects will be presented using actual sampling times. Graphical summary for mean data will be presented using nominal sampling times 
 The impact of any major deviation from the planned assessment times and/or scheduled visit days on the analyses and interpretation of the results will be assessed as appropriate. Reporting for Data Listings: 
 Planned and actual time relative to study drug dosing will be shown in . Unscheduled or unplanned readings will be presented within the subject's listings. 	
Unscheduled Visits	

 Unscheduled visits will be included in subject visit domain. 	
Descriptive Summary Statistics	
Concentration Data	Descriptive summary (mean, standard deviation, coefficient of variation, median, minimum and maximum) will be computed for each pharmacokinetic parameter for the test and reference products.
Graphical Displays	
Graphical summary for mean data will be presented using nominal sampling times.	

10.3.3. Reporting Standards for Pharmacokinetic

Pharmacokinetic Concentration Data	
PC Windows	Pharmacokinetic data will be calculated using the non-compartmental model by using statistical package SAS® 9.4.
Descriptive Summary Statistics, Graphical Displays and Listings	Descriptive summary (mean, standard deviation, coefficient of variation, median, minimum and maximum) will be computed for each pharmacokinetic parameter for the test and reference products. Graphical summaries for individual subjects will be presented using actual sampling times
Pharmacokinetic Parameter Derivation	
PK Parameter to be	The following PK parameters will be derived by the Programmer: C_{max} , AUC_{0-t} ,

Derived Programmer	by	AUC _{0-inf} , T _{max} , AUC _{0-t} /AUC _{0-inf} , Residual area, K _{el} , t _{1/2} , Vd, CL
Pharmacokinetic Parameter Data		
Descriptive Summary Statistics, Graphical Displays and Listings		N, arithmetic mean, median, min, max, SD will be provided for untransformed data. For log-transformed data, geometric mean, 90% CI of geometric mean, T/R ratio (%), mean square error (mse), , intra-subject variability, power of log-transformed data will be reported.
Untransformed PK parameter		tmax, AUC _{0-t} /AUC _{0-inf} , Residual area, K _{el} , t _{1/2} , Vd, CL, T _{lin} , Lqct,

10.4. Appendix 4: Derived and Transformed Data

10.4.1. Pharmacokinetic

PK

• Plasma sample analysis will be carried out by Accutest Research Laboratories (I) Pvt Ltd. Griseofulvin plasma concentrations will be determined using the currently validated methodology. The actual sampling times, will be used in the PK calculations.• Griseofulvin plasma concentration-time data will be analyzed by non-compartmental methods with SAS software version 9.4 and derived PK parameters will be summarized and listed. Derived Pharmacokinetic parameters will be summarized by treatment group. Mean, Median, Min, Max, SD for untransformed pharmacokinetic parameters• For log-transformed data, geometric mean, 90% CI of geometric mean, T/R ratio (%), mean square error (mse), , intra-subject variability, power of log-transformed data will be reported.• Graphical summary for mean data will be presented using nominal sampling times. Graphical summaries for individual subjects will be presented using actual sampling times.

10.5. Appendix 5: Reporting Standards for Missing Data

10.5.1. Premature Withdrawals

Element	Reporting Detail
General	
 Subject study completion (i.e. as specified in the protocol) was defined as completion of all phases of the study. Withdrawn subjects will be notreplaced in the study. All available data from participants who were withdrawn from the study will be listed and all available planned data will be included in summary tables and figures, unless otherwise specified.

10.5.2. Handling of Missing Data

Element	Reporting Detail
General	
Missing samples can be due to withdrawal of participant and accidental spillage of samples as mentioned in current version of SOP for 'Missing Sample'. Missing sample values (MSV) or non-reportable values (NRV), of the plasma concentration data, will be represented as MSV and NRV in the plasma concentration tables and reasons for their missing will be documented. Any BLQ value occurring between two measurable concentration values will also be treated as missing sample (MS). These missing values will be treated as 'missing values' for Pharmacokinetic and statistical analysis. All the procedures will be performed in accordance with current version of SOP for 'Calculation of Pharmacokinetic Parameters'. For participants with missing or non-reportable concentrations for three or more of the last samples, only the C_{max} and T_{max} will be presented and included in the statistical analysis. Other PK parameters will not be reported. Data from the participants with missing concentrations values (missed blood draws, lost samples, samples unable to be quantified) may be used if pharmacokinetic parameters can be estimated using the remaining data points. Otherwise, concentration data from these participants will be excluded from the final analysis.

Outliers	
 Any participants excluded from the summaries and/or statistical analyses will be documented along with the reason for exclusion in the clinical study report.

10.5.2.1. Handling of Missing and Partial Dates

Element	Reporting Detail		
General	
 Partial dates will be displayed as captured in case report forms of subjects Imputed partial dates will not be used to derive study day, time to onset or duration (e.g., time to onset or duration of adverse events), or elapsed time variables (e.g., time since diagnosis). In addition, imputed dates are not used for deriving the last contact date in overall survival analysis dataset. 		
Adverse Events	
 Imputations in the adverse events dataset are used for slotting events to the appropriate study time periods and for sorting in data listings. Partial dates for AE recorded in the CRF will be imputed using the following conventions: 
 
 Missing start day	 
 If study treatment start date is missing (i.e. participant did not start study treatment), then set start date = 1st of month. Else if study treatment start date is not missing: 
 If month and year of start date = month and year of study 	
 
 	Missing start day	
 If study treatment start date is missing (i.e. participant did not start study treatment), then set start date = 1st of month. Else if study treatment start date is not missing: 
 If month and year of start date = month and year of study
Missing start day	
 If study treatment start date is missing (i.e. participant did not start study treatment), then set start date = 1st of month. Else if study treatment start date is not missing: 
 If month and year of start date = month and year of study 		

Element	Reporting Detail	
		treatment start date then 
 ▪ If stop date contains a full date and stop date is earlier than study treatment start date then set start date= 1st of month. ▪ Else set start date = study treatment start date. ○ Else set start date = 1st of month.
	Missing start day and month	
 • If study treatment start date is missing (i.e. participant did not start study treatment), then set start date = January 1. • Else if study treatment start date is not missing: 
 ○ If year of start date = year of study treatment start date then 
 ▪ If stop date contains a full date and stop date is earlier than study treatment start date then set start date = January 1. ▪ Else set start date = study treatment start date. ○ Else set start date = January 1.
	Missing stop day	Last day of the month will be used.
	Missing stop day and month	No Imputation
	Completely missing start/end date	No imputation
	
 • Completely missing start or end dates will remain missing, with no imputation applied. 	
Concomitant Medications/ Medical History	
 • Partial dates for any concomitant medications recorded in the CRF will be imputed using the following convention: 	
	Missing start day	
 • If study treatment start date is missing (i.e. participant did not start study treatment), then set start date = 1st of month. • Else if study treatment start date is not missing: 
 ○ If month and year of start date = month and year of study treatment start date then 
 ▪ If stop date contains a full date and stop date is earlier than study treatment start date then set start date= 1st of month. ▪ Else set start date = study treatment start date. ○ Else set start date = 1st of month.
	Missing start day and month	
 • If study treatment start date is missing (i.e. participant did not start study treatment), then set start date = January 1. • Else if study treatment start date is not missing: 
 ○ If year of start date = year of study treatment start date then 
 ▪ If stop date contains a full date and stop date is earlier than study treatment start date then set start date = January 1. ▪ Else set start date = study treatment start date. • Else set start date = January 1.
	Missing end day	A '28/29/30/31' will be used for the day (dependent on the month and year)
	Missing end day and month	A '31' will be used for the day and 'Dec' will be used for the month.
	Completely missing start/end date	No imputation

Element	Reporting Detail
	
 
• The recorded partial date will be displayed in listings.
[Insert as required...]	

Concomitant medication details:

Drug Name (Brand Name)	Dosage form	Strength	Frequency	Start date	End date	Recorded By

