8.3.1. Time Period and Frequency for Collecting AE and SAE Information

- All SAEs will be collected from the start of treatment until the follow-up visit at the time points specified in the SoA (Section 1.3).
- Medical occurrences after obtaining informed consent but before the initiation of study treatment will be recorded on the Medical History/Current Medical Conditions section of the case report form (CRF) not the AE section.
- All SAEs will be recorded and reported to the sponsor or designee immediately and under no circumstance should this exceed 24 hours of occurrence of SAE, as indicated in [Appendix 3](#). The investigator will submit any follow up information to the sponsor within 24 hours of occurrence.
- Investigators are not obligated to actively seek AEs or SAEs after the conclusion of the study participation. However, if the investigator learns of any SAE, including a death, at any time after a participant has been discharged from the study, and he/she considers the event to be reasonably related to the study treatment or study participation, the investigator must promptly notify the sponsor.

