2.3. Study Design

Overview of Study Design and Key Features	

The diagram illustrates a three-period, three-treatment crossover study. It begins with 'Participants' who undergo 'Randomization' (indicated by a dashed box). The study is divided into three periods, each containing a single treatment. Period 1 (orange bar) includes treatments T1, T2, and R. Period 2 (blue bar) includes T2, R, and T1. Period 3 (red bar) includes R, T1, and T2. Washout periods are shown between Period 1 and 2, and between Period 2 and 3. A bracket labeled 'Period' encompasses the three treatment bars.
	

T1 = Griseofulvin Tablets, 500 mg Test Product T2 = Griseofulvin Tablets, 250 mg Test Product R = Griseofulvin Tablets, 500 mg (Grisovin) Reference
	
Design Features	
 This is an open label, randomized, balanced, three treatment, three period, three sequence, single dose, crossover study to evaluate the bioequivalence of test Griseofulvin tablets, 500 mg versus reference Griseofulvin tablets, 500 mg as well as dose proportionality of test Griseofulvin tablets, 250 mg and 500 mg, in healthy, adult participants under fed conditions. This study includes a screening period (within 21 days prior to dosing of period-I) and three open-label treatment periods. Participants will be followed up 5 days after last dosing. Each participant will receive all 3 treatments according to their assignment to one of 3 treatment sequences (T1T2R, T2RT1 or RT1T2).
Dosing	
 In each period, single oral dose [Test Product (T1): 1 x 500 mg Tablet or Test Product (T2): 1 x 250 mg Tablet or Reference Product (R): 1 x 500 mg Tablet] of the study treatments will be administered to the participants as per randomization with 240 ± 2 mL of water at ambient temperature under fed condition.
Time & Events	
 [Refer to Appendix 1: Schedule of Activities]
Treatment Assignment	
 The whole study will be divided into three periods. For each period, eligible participants will be randomized to either T1T2R, T2RT1 or RT1T2 treatment sequence according to 1:1:1 ratio.

Overview of Study Design and Key Features	
Interim Analysis	
 No interim analysis is planned.

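### Does the partial-date rule for adverse events put Period 2 and Period 3 events under the wrong product?

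*SAP*

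**What the plan says.** SAP 10.5.2.1 gives the purpose of imputing adverse-event dates: "Imputations in the adverse events dataset are used for slotting events to the appropriate study time periods and for sorting in data listings". With a missing start day, an event in the calendar month of first treatment falls to "Else set start date = study treatment start date", unless a full stop date shows that it ended before treatment began. In any other month it is set to the 1st. With day and month both missing, the test is "If year of start date = year of study treatment start date then". If that holds, the date again becomes the treatment start date, with the same stop-date exception; otherwise it becomes 1 January. No Period 2 or Period 3 dosing date enters the rule.

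The same section limits the use of the result: "Partial dates will be displayed as captured in case report forms of subjects", and "Imputed partial dates will not be used to derive study day, time to onset or duration".

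SAP 10.2.1, whose heading refers to study phases, defines none. It shows a blank adverse-event record with fields for study period, onset and reporting times, time of last dose, and "Last Investigational Medicinal Product Administered". SAP 2.3 states: "Each participant will receive all 3 treatments according to their assignment to one of 3 treatment sequences".

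**The concern.** In a three-period crossover, the period in which an event began determines the product it follows. A rule that slots events to periods but knows only the first dosing date cannot do that for later periods: it pulls them back to the first dose or to the start of a month.

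The crossover meaning is plausible. The adverse-event record has a study-period field. Protocol 8.3.1 also leaves little to sort before treatment: "Medical occurrences after obtaining informed consent but before the initiation of study treatment will be recorded on the Medical History" section of the case report form.

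The secondary objective is the safety and tolerability of T1, T2 and R. If product were read from the slotted period, events would be counted under the wrong product, and no sentence in the SAP says that the recorded product outranks the imputed date.

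**Working it through.** **Inputs.** Doses fall on nominal Days 1, 8 and 15, with 7 to 14 days allowed between doses (Protocol 1.3 and 4.1). Follow-up is 5 days after the last dose (Protocol 4.1). The imputation rule is that of SAP 10.5.2.1. As a check on the schedule, Day -1 to Day 19 with no Day 0 is 20 calendar days, which agrees with the duration in Protocol 1.1.

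**Assumptions, not in the documents.** First-dose dates are spread evenly over a 365-day year. Onset days are spread evenly over a window of L days starting at the dose. The study time periods are taken to be the crossover periods.

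**Missing start day.** A Period 2 or 3 event is placed correctly only if the 1st of a month falls between that period's dosing day and the onset day, both included. Otherwise the imputed date precedes the period's dose. For onset j days after the dose, the chance is 12(j + 1)/365. Averaged over j = 0 to L - 1:

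share wrong = 1 - 12(L + 1)/(2 × 365)

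| Window L (days) | Share wrong |
|---|---|
| 2 | 1 - 36/730 = 95.1% |
| 5 | 1 - 72/730 = 90.1% |
| 7 | 1 - 96/730 = 86.8% |
| 10 | 1 - 132/730 = 81.9% |
| 14 | 1 - 180/730 = 75.3% |

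With Period 2 as long as the dose gap and Period 3 of 5 days, weighted by days:

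- 7-day gap: (7 × 86.8 + 5 × 90.1)/12 = 88.2%
- 10-day gap: (10 × 81.9 + 5 × 90.1)/15 = 84.7%
- 14-day gap: (14 × 75.3 + 5 × 90.1)/19 = 79.2%

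If Period 3 lasts as long as the gap, the shares are 86.8%, 81.9% and 75.3%. Running the rule date by date over a year gives the same values. Period 1 events are never misplaced.

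**Spread behind the averages.** With even onset and a 5-day Period 3:

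- Doses on 6, 13 and 20 January: every Period 2 and 3 event is set to 6 January, so 12 of 12 onset days are wrong (100%).
- Doses on 18 January, 1 February and 15 February: all 14 Period 2 days are set to 1 February, which is right. The 5 Period 3 days are also set to 1 February, which is wrong: 5/19 = 26%.

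**Day and month missing.** Every same-year Period 2 or 3 event goes to the first dose date, so 100% are wrong. The year changes for only 3% to 8% of these events. The rule then uses 1 January, and 70% to 93% are wrong.

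**The other meaning.** If the periods are before and after first treatment, the imputed date of a Period 2 or 3 event is the first dose date or later. It is on treatment, as it should be: 0% misplaced.

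**Which outputs use the slot.** SAP 6.4.3 promises collective incidence and SAP 10.8.4 an adverse-event listing. SAP 7 plans no formal safety analysis. SAP 7.1 defers the rest to the contract research organisation's standards, which are not reproduced. No table by product built from slotted dates is specified.

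**The case for a change.** The strongest case for a change is that the rule cannot serve its stated purpose under a reasonable reading, that the arithmetic is not in dispute, and that a sentence would cure it. The secondary objective concerns each product, and the deferred standards cannot be inspected, so a reader cannot confirm that no by-product table draws on slotted dates.

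Part of this stands. The term is undefined, the precedence between recorded and imputed information is unstated, and the crossover reading is possible.

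The rest is weaker. The rule's branches ask only whether treatment was started and whether the event ended before it; neither helps to separate crossover periods. The phases heading concerns treatment-emergent events. The surrounding text is template wording: it mentions an overall survival dataset and time since diagnosis, which have no place in this trial. The adverse-event row in the schedule of activities also appears to start at the Day -1 check-in, as far as the extracted table shows. If so, a split before and after the first dose has something to do, despite Protocol 8.3.1.

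The information needed for attribution is already recorded. Each product is given once per participant, so the last product given identifies the period. One caution remains for whoever uses that field: the record has both onset and reporting times, so it must be read as the last dose before onset, not before reporting.

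**Conclusion.** No change to the plan is needed. The figure of 75% to 95% is right as a conditional average, but it rests on the crossover reading, on evenly spread first-dose dates, on assumed onset patterns and on a missing start day. Participants dosed on the same day could see anything from 26% to 100%. Under the reading that the rule's branches support, the figure is 0%.

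Even on the adverse reading, no specified output is shown to be wrong. Raw partial dates stay visible, imputed dates do not feed study day, onset or duration, and the recorded period and product allow direct attribution.

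The documents do not give the number of partial dates, and it may be zero. Participants are housed to 24 hours after each dose and seen on three further days per period, and data cleaning precedes analysis (SAP 3.1). Any misplacement would blur product differences in a descriptive summary; with 1:1:1 sequences it would favour no product in expectation. The pharmacokinetic conclusions on bioequivalence and dose proportionality are untouched.

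This is a gap in wording that an analyst fills sensibly by attributing events from the recorded product and period. A sentence defining the study time periods would be tidy, but the results do not depend on it.
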